Study Protocol:

Supplemental enteral protein in critically ill trauma and surgical patients: A randomized clinical trial

NCT03170401

December 15, 2023

This document provides a description of the study protocol and analysis plan for this clinical trial.

1. Overall design and conduct of this single center clinical trial.
2. Data safety and monitoring plan.
3. Modification to the study protocol specifically regarding pauses in enrollment and additional evaluation of safety and adverse events.
4. Names and responsibilities of the study team members.
5. Study sponsorship.
6. Citations for study description and protocol.

1 Overall design and conduct of the clinical trial

This is a single center, randomized clinical trial in which critically ill trauma victims and surgical patients are identified, recruited, and randomized to either standard enteral nutritional support or to treatment with early supplemental enteral protein to a target amount of 2gm/kg/day. The treatment protocol/intervention was designed, tested and reported in a prospective, observational cohort study of 53 critically ill surgical patients.¹

1.1 Background and rationale

Observational studies suggest that higher amounts of protein are associated with better outcomes in critically ill patients. However, clinical trials addressing the question of protein dosing in critically ill trauma patients have not been performed. Based upon expert opinion in addition to observational data, the 2016 ASPEN guidelines recommended that critically ill patients should receive 1.2 – 2.0 gm/kg/day of protein and potentially higher amounts in critically ill trauma and burn patients.² Our trial is designed to test this hypothesis in trauma and surgical patients by randomizing to early supplemental enteral protein or to standard enteral nutritional support.

1.2 Primary Research Question

In critically ill trauma and surgical patients does receiving a higher amount (≥ 2.0 grams/kg/day) of protein compared to usual care (~ 1.0 gram/kg/day) improves biomarkers of nutritional status (serum transthyretin concentration) and short-term clinical outcomes (ventilator-free days and ventilator-associated pneumonia).

1.3 Study hypotheses

Compared to receiving standard enteral nutritional therapy, the administration supplemental enteral protein to target a total protein intake of 2 gm/kg/day leads to higher serum transthyretin

concentrations during the 3rd week after admission to the intensive care unit and increase the number of ventilator-free days.

1.4 Trial design

A single center, randomized, open-label, clinical trial including subjects admitted to the trauma/surgical intensive care unit at Harborview Medical Center in Seattle, Washington, USA. A CONSORT style flow diagram will present the numbers of patients screened and all reasons excluded prior to randomization. This figure will also present the number randomized to each arm and the numbers included in the assessment of outcomes.

1.5 Eligibility criteria:

Published at [https://clinicaltrials.gov/ct2 Study Details | Supplemental Enteral Protein in Critical Illness | ClinicalTrials.gov/show/NCT03160547](https://clinicaltrials.gov/ct2/Study%20Details%20%7C%20Supplemental%20Enteral%20Protein%20in%20Critical%20Illness%20%7C%20ClinicalTrials.gov/show/NCT03160547).

1.6 Study procedures

Screening of all potential subjects will be done by the Registered Dietitian who is assigned to the Critical Care team and is a member of the research team. Potential study subjects will be identified upon admission to the critical care unit and considered for enrollment if they meet inclusion criteria. Once a subject has been identified, we will randomize that subject into one of the two treatment arms. We will randomly assign subjects to receive either additional enteral protein to achieve a total of 2g/kg/day of protein or to standard enteral nutritional support. Due to the limited published information and the variation across hospitals and within our own practice, both treatment groups can be considered standard care. At Harborview, there is no protocol utilizing one method of protein dosing vs the other. Both are approaches used in our critically ill surgical and trauma patients. The University of Washington Institutional Review Board has approved this study with a waiver of documented consent as it is considered minimal risk (.

We will use a **randomized design** to test whether supplementing enteral protein improves patient care and outcomes. Subjects will be followed until discharged from the hospital and clinical data will be obtained from the electronic medical record. The randomization will be done by previously sealed envelopes that contain an equal number of each treatment assignment. Subjects are randomized 1:1 to either no or additional enteral protein.

Standard of care at our institution includes obtaining nutrition-related labs. Vitamin C, Vitamin D, Zinc and other vitamins and micronutrients are typically measured within 24 hours of ICU admission and used to guide supplementation and treat any deficiencies. Circulating transthyretin (TTHY), C-reactive protein (C-RP) are measured approximately weekly in patients requiring greater than 7 – 10 days of nutritional support. Similarly, we often obtain urine for 24-hour total urinary nitrogen (TUN) measurements, and indirect calorimetry (this is a measure, not a lab procedure) after 7 – 10 days of support. Indirect calorimetry is used to adjust caloric intake and to better understand a patient's general use of energy sources. In this trial the dietitian and

clinical team may adjust caloric goals based upon indirect calorimetry. We will not adjust protein intake based upon TUN or TTHY measurements.

In a subgroup of study subjects, we will also obtain serial blood and urine samples for analyses of metabolites. Each blood sample collected will be 5ml and each urine sample will be 100ml. The samples will be obtained on Day 0 (defined as the day nutritional support is initiated), Day 1 (24 hours later), Day 3 (72 hours later +/- 24 hours), Day 7-13, Day 14-20, Day 21-27, Day 28-34. If the subject is discharged prior to any of these timepoints, we would obtain the final sample on the day of discharge. Only one sample will be collected during the above timepoints.

[figure not shown]
Urine will be collected from the subject's indwelling catheter, if they do not have an indwelling catheter, no urine samples will be obtained. Blood samples will be obtained through an existing IV catheter if possible. If the subject does not have an existing IV catheter, we will obtain the sample by venipuncture by either the bedside RN or the research RN. We have found that without the ability to obtain the samples by venipuncture (with the subject's permission), we are not able to collect the later samples, and this is affecting the data analysis. We will stop all urine collection when the indwelling catheter has been removed. The blood and urine samples will be analyzed for approximately 200 metabolites as well as inflammatory biomarkers.

Patients will be screened, evaluated, and randomized within 96 hours of admission to the ICU by the study dietitian with guidance from the principal investigator in the case of uncertainty whether the patient qualifies. Subjects will be randomized 1:1 to either supplemental enteral protein or standard enteral nutritional support. Randomization is performed using sealed envelopes with the treatment assignment.

1.7 Sample Size Considerations

[figure not shown]
Sample size calculation and statistical analysis of circulating transthyretin concentrations

(Primary hypothesis): With 500 participants this study has 80% power to detect a difference of 2.4 mg/dl in average circulating transthyretin levels during the third week between the protein supplementation group (assumed average circulating transthyretin level of 14.4, and the standard of care group (assumed average circulating transthyretin level of 12.0, with a pooled standard deviation of 7.0). This conservatively assumes that there will be 25% of the patients for whom the protein supplementation has no effect in that they are either well enough to have high circulating transthyretin levels or die prior to obtaining the primary outcome. Because the

primary outcome is a surrogate marker, we do not plan for any formal interim analyses to evaluate efficacy or futility. Harborview Medical Center typically admits about 300 - 350 trauma victims per year who would meet eligibility criteria. With enrollment over 4 - 5 years, we anticipate that ~1500 patients will be eligible. Therefore, the rate of recruitment among eligible patients needs to be ~33%. The statistical analysis of the primary hypothesis will use a two-sided t-test with alpha of 0.05. We expect that less than 10% of patients will die prior to day 21. For these and for patients who are lost-to-follow-up prior to day 21, we will multiply impute the primary outcome separately for each group and incorporate previously observed circulating transthyretin levels (if available) and patient age information.

Power calculation and statistical analyses of ventilator-free days (VFDs; secondary hypothesis): VFD is a relevant endpoint in critical care and critical care research. We will use this endpoint as our main clinical outcome as it generally reflects the development of complications and provides an objective estimate of the rate of recovery. VFD could be expected to be impacted by nutritional support in several important ways. The adjacent figure represents the difference in VFD between the groups that we have 80% power to detect for a range of pooled VFD standard deviations and assuming no loss to follow-up (LTFU), 15% LTFU and 25% LTFU, based upon the sample size selected for the primary hypothesis ($n = 500$). For patients who die while in the hospital, VFDs will be set to zero. For patients who are lost to follow-up (unlikely), VFDs will be multiply imputed separately by treatment group, using patient age and measures of injury severity (injury severity score, AIS scores).

1.8 Interim analyses

There are no planned interim analyses for this study and no early stopping rules were designed.

1.9 Timing of final analysis

All outcomes will be analyzed by arm once all data is collected, data cleaning is complete and after the statistical analysis plan (SAP) is finalized. See modifications to the study protocol for details regarding the final timing of data analysis that was based upon additional collection of data related to potential complications of the treatment intervention.

1.10 Timing of outcome assessments and recording of nutritional intake

All outcome assessments are based upon data from the index hospitalization. Daily nutrition intake was assessed only for up to a maximum of 28 days in the ICU. This included daily enteral formula type and volume, daily enteral caloric and protein intake, and daily intravenous fat (as propofol) and glucose calories administered.

1.11 Confidence intervals and p-values

95% confidence will be presented for selected key outcomes. P-values will be two-sided without adjustment for multiplicity. We will use the traditional two-sided $p \leq 0.05$ to indicate statistical significance for the primary and other prespecified outcomes. For subgroup analyses we will report only confidence intervals.

1.12 Description of general nutritional support for trial subjects

Our approach to nutritional support and monitoring for subjects in this trial will follow the general approach that has been used in our intensive care unit and reported previously.³⁻⁵ Once deemed ready to receive enteral nutrition, the patient is prescribed an isotonic formula with 1 – 1.5 kcal/ml. Continuous infusion starts at 20 ml/hour and the rate is advanced over 24 hours to an initial goal of 25 kcal/kg/day delivered by continuous infusion via an orogastric or nasogastric tube. Subsequent modifications of caloric and other nutritional prescriptions are performed by the ICU dietitian and include use of the Harris-Benedict equation and indirect calorimetry in appropriate patients after 5 – 7 days of mechanical ventilation. Monitoring for intolerance is primarily by clinical examination. Diarrhea is managed first but modifying the enteral formula to include higher fiber and testing for *C. difficile* infection.

1.13 Description of enteral protein supplementation treatment

The dietitian will calculate energy and protein needs as indicated in *1.11* above. For subjects randomized to the supplemental protein, arm 2 gm/kg/day of Prosource (Medtrition, Lancaster, PA) will be administered via the nasal/oral feeding tube in 60 – 180 ml bolus infusions 2 – 4 times per day, independently of the enteral formula received. That is, the daily target amount of protein will be administered as supplement boluses beginning on the day the patient is enrolled. Once the enteral formula infusion approaches the target rate then the amount of supplemental protein will be gradually decreased. Supplemental protein will be reduced by 50% once the patient received 75% of targeted caloric intake over the previous day (0700 – 0700). Once the patient reaches the target caloric intake for 48 continuous hours, the amount of supplemental protein will be decreased in order that the total protein prescribed equals 2 gm/kg/day.

2 Data safety monitoring plan

Safety of our intervention will be reviewed by an independent Data Safety Monitoring Board (DSMB) after at 2 timepoints during the trial. The committee will include surgical intensivists who also have experience with clinical and translational research. Data for review will be

prepared by the study analyst ([name]) and study biostatistician ([name]). The review will be iterative. After review of the summary information, additional data from the EMR can be added at the request of the members. Members will also have access to individual patient/study subject records as needed for additional details.

3 Modifications to the study from initial protocol

3.1 Enrollment pauses

There were 3 pauses in subject enrollment over the course of the clinical trial. The first pause was from August 8th – 27th, 2019. This pause was necessary while waiting for approval from the IRB for an updated blood sampling strategy that included more frequent blood sampling. The second pause was due to the COVID-19 pandemic, and we were required to stop non-critical activities at our hospital for 2 ½ months (3/10/2020 – 5/24/2020). Enrollment was also paused for 3 ½ month period while the hospital transitioned to a new electronic health record (EHR). This new EHR included a mechanism to record patient enrollment into clinical trials and we paused enrollment until that system was functional.

3.2 Update to Institutional Review Board approval – August 2019

On August 23, 2019, the protocol was updated following review by the full IRB committee. The IRB had initially provided this approval using the process of “expedited review”. When the study approval was migrated from the original “paper”-based format to the new Zipline, electronic format the IRB determined that review by the entire committee was required to permit waiver of documented consent for the frequency of blood sampling that we requested. This oversight on the part of the IRB led to a pause in enrollment from August 6th – 27th, 2019 (first pause described in 3.1).

3.3 Expansion of data collection procedures

In 2021, as we were approaching complete enrollment, we obtained approval from the University of Washington IRB to obtain data from the electronic medical record and from the institutional quality improvement databases to provide additional information regarding hospital acquired infections and other complications for study subjects. At this time, the IRB also approved our request to obtain a minimal dataset for patients who were potentially eligible but who were not enrolled in the trial. We included the following request in our modification: “We are requesting permission to retrospectively and prospectively enroll subjects who meet inclusion/exclusion criteria but are not planned for randomization. We are requesting permission to obtain this data from the retrospective group to the start of this study. We will identify patients who met enrollment criteria, but were not randomized, beginning on 11/17/2016 (date first randomized subject was enrolled) through the present date. For these retrospectively identified subjects, we will obtain data from the EMR. Prospective: Beginning with approval of this MOD, we will

collect data from the EMR from patients who met enrollment criteria, but not randomized. This group will be identified prospectively, and data collected upon discharge from the hospital. The purpose of obtaining information for these eligible, but not randomized subjects is to be able to create an accurate CONSORT diagram, which will be required for reporting/publication of any data from this trial. This information will also be helpful for future grant submissions.”

3.4 Additional assessments of adverse events and complications

Following the completion of enrollment, initial data collection and analyses, we observed more respiratory adverse events in the supplemental protein treatment arm than the control arm (see manuscript Table 3: Safety, complications, and adverse events). Both reintubation rates and possible aspiration rates were higher. To better understand whether subjects had aspirated gastric contents, the timing of this aspiration, whether it caused deterioration in gas exchange or lead to pneumonitis or pneumonia, we reviewed the medical records directly. Briefly, 2 co-investigators independently reviewed medical records and were asked to “adjudicate” whether a subject had clear evidence of tracheobronchial aspiration of gastric contents. All instances of reintubation or possible aspiration (see eMethods for definitions) were reviewed. Adjudicated aspiration was assigned if there was consensus assignment by the 2 reviewers. If there was disagreement, a third, independent reviewer made the assignment. All reviewers were blinded to the treatment assignment. These reviews were conducted from 1/4/2023 – 4/1/2023. The data were then merged with the research database and submitted to a study statistician ([name]) for analysis.

4. Names and responsibilities of the study team members

[name]. Professor of Surgery, University of Washington. Lead investigator. Obtained funding from NIGMS, Designed the trial and co-designed the treatment intervention with [name]. Oversaw study subject enrollment and assisted with determination of potential study subject eligibility. Responsible for reviewing all data analyses and drafting the manuscript.

[name]. Senior Research Scientist. Department of Biostatistics. University of Washington. Created the statistical analysis plan in consultation with [name] and [name]. Conducted the statistical analyses for the manuscript and prepared the summary tables based upon these analyses. Also performed critical review of the manuscript.

Statistical Analysis Plan:

**Supplemental enteral protein in critically ill trauma and surgical patients: A
randomized clinical trial**

NCT03170401

August 20, 2023

1. Trial Synopsis

The aim of this study is to determine the effect of enteral protein supplementation on biochemical measures of inflammation and protein metabolism in critically ill surgical patients. The investigators will also collect data on important clinical outcomes, including infectious complications, duration of mechanical ventilation and other measures of recovery from critical illness.

Overall Hypothesis: That early supplemental enteral protein will increase serum concentrations of transthyretin at three weeks after the onset of illness or injury. Secondarily, we will test whether supplementation increases ventilator-free days and reduces ventilator-associated pneumonia.

2. Primary Objective

Overall Aim: To determine the effect of enteral protein supplementation on serum protein markers, ventilator-free days, and complications in critically ill trauma victims.

Primary Hypothesis: That early supplemental protein will increase serum concentrations of transthyretin at two weeks after injury.

Secondary hypothesis: that supplementation improves clinical outcomes shown by an increase in ventilator free days (reduced duration of mechanical ventilation).

3. Design

The trial will use an open label parallel randomized trial design with a planned 500 patients receiving enteral nutrition randomized 1:1 to 2 g/kg/day of protein vs standard care.

4. Primary Estimand Statement¹

Population: critically ill adult trauma patients who are started on enteral nutrition within 72 hours after injury and are expected to require nutritional support for at least 1 week. Non-trauma post-surgical patients meeting study entry criteria will be included as well. This is expected to include patients recovering from emergency surgery, including amputations, debridement of necrotizing soft-tissue infections, and other serious surgical illnesses.

Treatments: Enteral protein with a target rate of 2 g/kg/day vs standard enteral nutrition.

Variable of Interest: Circulating transthyretin at 3 weeks (14-21 days after injury)

Primary efficacy analysis population definition: All randomized participants

Intercurrent events: Subjects may be missing transthyretin due to death, discharge from the hospital, or recovery. Those participants who die will have a transthyretin level equal to the lowest value observed amongst the surviving subjects. Participants who are discharged alive

from the hospital before the primary outcome is measured will have a transthyretin level set equal to the highest observed measure. Multiple imputation will be used to account for study participants who did not have transthyretin measured in the expected window.

Summary measure: The difference in mean transthyretin levels between treatment arms.

5. Study Population

The investigation will enroll 500 subjects using the following inclusion and exclusion criteria:

Inclusion: critically ill adult trauma patients who are started on enteral nutrition within 72 hours of admission to the intensive care unit and are expected to require nutritional support for at least 1 week. Non-trauma post-surgical patients meeting study entry criteria will be included as well. This is expected to include patients recovering from emergency surgery, including amputations, debridement of necrotizing soft-tissue infections, and other serious surgical illnesses.

Exclusion: An individual who meets *any* of the following criteria will be excluded from participation in this study:

- Significant chronic organ failure,
- severe malnutrition,
- not expected to survive due to severity of injuries and,
- serum creatinine >2 mg/dl.

6. Data sources

Data will be collected concurrently with study subject enrollment and treatment in the intensive care unit. extracted from the electronic medical record.

7. Outcomes

7.1 Primary endpoint:

Circulating transthyretin concentrations measured 14 – 21 days after injury.

7.2 Secondary endpoint:

- Ventilator free days: the numbers of days on which the subject does not require assisted ventilation during the first 28 days following the date of injury. VFD will be set to zero for all participants who die before hospital discharge.
- Hospital acquired pneumonia: Pneumonia diagnosed while the patient is in the hospital. Pneumonia will be defined as the presence of a positive quantitative culture from a bronchoalveolar lavage sample coupled with the use of antibiotics.

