8.5 Primary Statistical Hypothesis

The null hypothesis is that the mean circulating transthyretin level, measured between days 14 and 21, in the group of subjects randomized to the intervention arm is equal to the mean in the control group.

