With 500 participants this study has 80% power to detect a difference of 2.4 mg/dl in average circulating transthyretin levels during the third week between the protein supplementation group (assumed average circulating transthyretin level of 14.4, and the standard of care group (assumed average circulating transthyretin level of 12.0, with a pooled standard deviation of 7.0). This conservatively assumes that there will be 25% of the patients for whom the protein supplementation has no effect in that they are either well enough to have high circulating transthyretin levels or die prior to obtaining the primary outcome. Because the primary outcome is a surrogate marker, we do not plan for any formal interim analyses to evaluate efficacy or futility. Safety of our intervention will be reviewed by an independent Data Safety Monitoring Board (DSMB) on a regular basis. Currently, the Harborview Medical Center typically admits about 300 - 350 trauma victims per year who would meet eligibility criteria. With enrollment over 4 - 5 years, we anticipate that ~1500 patients will be eligible. Therefore, the rate of recruitment among eligible patients needs to be ~33%. The statistical analysis of the primary hypothesis will use a two-sided t-test with alpha of 0.05. We expect that less than 10% of patients will die prior to day 21. For these and for patients who are lost-to-follow-up prior to day 21, we will multiply impute the primary outcome separately for each group and incorporate previously observed circulating transthyretin levels (if available) and patient age information as well as sex, race/ethnicity, NUTRIC score, and ventilator free days.

10. Statistical and Data Programming

All data cleaning and programming will be done in either the statistical software R (R Foundation) or in SAS (SAS).

References (for this document: Statistical Design and Power)

2. Rubin DB. *Multiple imputation for nonresponse in surveys*. Wiley series in probability and mathematical statistics Applied probability and statistics,. Wiley; 1987:xxix, 258 pages.

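### The tested pneumonia endpoint has no start at randomization, so earlier cases are not excluded; the primary-hypothesis date and the non-trauma day 0 also need wording fixes

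*SAP*

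**What the plan says.** **Pneumonia.** SAP section 7.2 defines hospital-acquired pneumonia as a diagnosis made during the hospital stay, shown by a positive quantitative lavage culture together with antibiotic use. It gives no starting date. Protocol 1.10 bases every outcome on the index hospitalization, and Protocol 1.6 lets randomization happen up to 96 hours after ICU admission. The exclusions in SAP section 5 do not mention existing pneumonia. SAP 8.7 compares the proportions by a score test, and SAP 8.11 assigns an alpha of 0.05 to secondary comparisons. Protocol 1.2 and SAP section 1 name ventilator-associated pneumonia instead.

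**Primary timepoint.** SAP section 2 gives the primary hypothesis as "That early supplemental protein will increase serum concentrations of transthyretin at two weeks after injury". SAP 7.1 defines the endpoint as "Circulating transthyretin concentrations measured 14 – 21 days after injury", SAP section 4 has the same window, and SAP 8.5 tests the mean "measured between days 14 and 21". SAP section 9 powers the trial on the third week.

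**Day 0.** SAP sections 4, 7.1, 7.2 and 7.5 count the primary window, ventilator-free days (VFD) and ICU-free days from injury. SAP section 1 has "increase serum concentrations of transthyretin at three weeks after the onset of illness or injury", and Protocol 1.3 has "concentrations during the 3rd week after admission to the intensive care unit". On who is enrolled, SAP sections 4 and 5 both say: "Non-trauma post-surgical patients meeting study entry criteria will be included as well".

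**Entry wording.** The 72-hour limit for starting enteral nutrition runs from injury in SAP section 4 and from ICU admission in SAP section 5.

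**The concern.** A pneumonia diagnosed before randomization cannot be affected by the assigned treatment. If it is counted, it adds the same expected number of events to each arm, pulls the risk ratio toward 1 and adds noise to a tested comparison.

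The remaining points are smaller. A primary hypothesis should carry the same date as its endpoint. Patients enrolled after, for example, a necrotizing infection have no injury date, so the analyst must choose an origin for three outcomes after the data exist. Transthyretin is drawn about weekly (Protocol 1.6), and patients discharged alive before measurement receive the highest observed value (SAP section 4). Moving the origin can therefore change which sample qualifies and who receives an assigned value.

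**Working it through.** **The plan's own figures.** The documents state no power for pneumonia, so there is nothing to reproduce on the main point. The stated 80% power for transthyretin has no time input and is unaffected. With 25% of patients showing no effect, the difference is 0.75 × 2.4 = 1.8; with SD 7.0 and 250 per arm, power is 82%, close to the stated figure.

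**Inputs for pneumonia.** From the documents: 500 patients randomized 1:1 (250 per arm) and two-sided 0.05. Assumed: post-randomization risks p of 20% versus 15%, or 30% versus 20%, and a share q of patients in both arms with pneumonia before randomization.

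**Formulas.**
- Counted risk under the present definition: q + (1 − q)p.
- Counted risk if only post-randomization cultures count, and patients with a prior case have no second event: (1 − q)p.
- Power = Φ[(|p₁ − p₂| − 1.96 s₀)/s₁], plus a negligible opposite tail. Here s₀ = √[2p̄(1 − p̄)/250], with p̄ the mean of the two risks, and s₁ = √[(p₁(1 − p₁) + p₂(1 − p₂))/250].

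**Example, 20% versus 15%, q = 5%.** Present definition: 0.05 + 0.95 × 0.20 = 24.0% and 0.05 + 0.95 × 0.15 = 19.25%. The ratio is 0.802, s₀ = 0.0368, s₁ = 0.0368, and power is 25.2%. With the date rule: 19.0% and 14.25%, ratio 0.75, s₀ = 0.0333, s₁ = 0.0332, power 29.7%.

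| q | Risks as written | Ratio | Power as written | Power with date rule | Gain (points) |
|---|---|---|---|---|---|
| 0% | 20.0 vs 15.0 | 0.75 | 31.2% | 31.2% | 0 |
| 1% | 20.8 vs 15.85 | 0.762 | 29.8% | 30.9% | 1.1 |
| 2% | 21.6 vs 16.7 | 0.773 | 28.5% | 30.6% | 2.1 |
| 5% | 24.0 vs 19.25 | 0.802 | 25.2% | 29.7% | 4.5 |
| 10% | 28.0 vs 23.5 | 0.839 | 21.0% | 28.1% | 7.1 |

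For 30% versus 20%, power with no prior cases is 73.4%. At q = 2%, 5% and 10% it is 70.1%, 65.1% and 57.5% as written, and 72.3%, 70.5% and 67.4% with the date rule.

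The absolute difference is (1 − q)(p₁ − p₂) under both definitions. The date rule therefore gains power by removing noise. It restores the risk ratio but not the full difference, because patients with a prior case stay in the denominator.

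**Timepoint.** Days 14 to 21 or the third week appears in SAP sections 4, 7.1, 8.5 and 9. SAP section 2 is the only one that differs, and no analysis is defined at two weeks.

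**Day 0.** SAP section 1 and Protocol 1.3 suggest different anchors, and neither is carried into an endpoint definition. The non-trauma share is not given. At an assumed 5%, 10% or 20%, 25, 50 or 100 of 500 patients would lack a defined window. This counts patients affected and says nothing about the size of the effect on the transthyretin difference.

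**Window length.** 21 − 14 + 1 = 8 days. Draws exactly 7 days apart both qualify only if they fall on days 14 and 21, one of seven alignments. Looser weekly timing could change that frequency, and no rule says which sample counts.

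**The case against.** The SAP never says that pneumonia before randomization counts; this is inferred from a missing start date. Protocol 1.5 places eligibility in a registry record that is not available here, and an exclusion for existing pneumonia there cannot be ruled out. Ninety-six hours is an upper limit, and the endpoint requires a culture plus antibiotics, so prior cases may be few. Every rate above is assumed, and at 1% to 2% the gain is 1 to 2 points in a comparison that has only 31% power to begin with. All of this stands and limits both size and certainty. It does not supply a start date, and a hospital-acquired label does not exclude the days in hospital before randomization.

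The more serious objection concerns timing. Protocol 3.4 reports that respiratory adverse events by arm had been seen, and that records were then reviewed for aspiration and any resulting pneumonia. Narrowing the pneumonia definition after that is a late change to a closely related outcome. This also stands, and it is why the any-in-hospital count must remain in the report.

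On the smaller points, the planned trauma-only subgroup already repeats the primary analysis where the injury date exists, so it is a partial check on the missing origin. The 72-hour wording concerns entry; enrollment is complete and all randomized patients are analyzed, so it changes no result.

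**Conclusion.** The pneumonia point holds as a gap in the definition: events before randomization are not excluded. The consequence is dilution, of about 1 to 7 power points at 20% versus 15% with prior cases in 1% to 10%. This assumes equal prior shares in both arms, no second event in patients with a prior case, and no relevant exclusion in the registry record. Confidence is moderate.

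Three stronger readings are tempting and are not supported:
- **That the definition biases the comparison toward one arm.** Prior events precede assignment, so randomization balances them in expectation.
- **That the primary window is unidentifiable.** SAP sections 4, 7.1 and 8.5 agree on it. The missing day 0 affects non-trauma patients only, its effect cannot be computed, and it also precedes randomization, so no between-arm bias follows.
- **That transthyretin by arm had been examined before these definitions were settled.** Protocol 3.4 reports respiratory events and does not say this, and Protocol 1.9 places outcome analysis after the SAP is final.

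**What to change.** **Main change.** In SAP 7.2 and 8.7, count as events only pneumonias whose diagnostic lavage culture was taken after randomization. Apply the rule by date, blind to arm. Report the any-in-hospital count alongside, and disclose that the change follows the respiratory findings by arm in Protocol 3.4.

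**Minor changes.**
- Replace two weeks in SAP section 2 with days 14 to 21.
- State one day 0 for non-trauma patients and use it for the primary window, VFD and ICU-free days. Onset of illness (SAP section 1) and ICU admission (Protocol 1.3) are the anchors already in the documents. Align SAP section 1 and Protocol 1.3 with the choice.
- State which transthyretin sample counts when two fall in the window.
- Use one pneumonia name and definition in both documents.
- Reconcile the 72-hour wording of SAP sections 4 and 5.

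**Cost.** Wording in both documents, a date recode for non-trauma patients, and a culture-date filter. At the assumed 2% to 10%, 10 to 50 of the 500 patients have a prior case that would leave the event count. No new patients or visits are needed. The real cost is that the pneumonia definition changes late, which the parallel count and the disclosure address.
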